The total blood volume drawn from a subject over the course of the entire study (48 months) will range from approximately 66 mL (in the case of no flare-ups) to 182 mL (in the case of two expected flare-ups treated per year, or a total of eight flare-ups treated during the entire study). In the event that the total drawn blood volume exceeds the limits established by the clinical site for pediatric subjects, then priority will be given to the key safety laboratory tests, as outlined in the clinical safety laboratory manual. This will ensure that the total blood volume drawn is within the established limits.

The Investigator will be provided all laboratory results and will review and assess out-of-range findings for clinical significance. Any post-baseline abnormal laboratory value assessed as clinically significant will be recorded as an AE. It is recognized that performing phlebotomy in subjects with FOP is very challenging due to their multiple ankyloses and the potential to cause injury resulting in a flare-up following multiple attempts. The Investigator will be notified about any protocol-specified safety laboratory test that could not be obtained despite at least two attempts. Should this occur, or for those samples that were drawn but were not usable (eg, quantity not sufficient, clotted, sample lost, etc.), the Investigator will assess the subject's condition and determine whether repeated attempts should be made to obtain the missing

laboratory data for that time point, or reassessed at the next scheduled time point based on the subject’s current clinical status (eg, AEs, vital signs) and previous laboratory measures.

Table 5 presents the clinical laboratory parameters that will be assessed in this study.

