1.10.3 Statistical Modifications to the Statistical Analysis Plan, V1.2

SAP Version 1.2 introduces the following changes:

- Clarifies that drawing subject-level rates of body regions with new HO from a gamma distribution and then drawing from Poisson distributions using these subject-level rates implies that the marginal distribution of the number of body regions with new HO follows a negative binomial distribution, which requires much less restrictive assumptions than a Poisson distribution and does not tend to result in an underestimate of the variance.
- Notes that additional details of the operating characteristics of the Bayesian compound Poisson analysis, including its chance of producing erroneous conclusions and the reliability of treatment effect estimates, will be included in a separate simulation report.
- Clarifies the secondary and exploratory endpoint definitions to add timepoints at which the endpoints will be compared between NHS and MOVE.
- Clarifies the definitions of treatment-emergent AEs and post-treatment AEs.
- Removes summaries of retinoid-associated AEs, as they already appear in the AE tables.
- Clarifies that a listing of traumas leading to flare-up will be generated.
- Adds summaries of imaging performance, i.e., intra-reader agreement and inter-reader agreement, and quality metrics.
- Adds summaries of dosing compliance.
- Clarifies the wLME analysis method by adding pseudocode.
- Clarifies the methods used to prepare the dataset for application of the Bayesian compound Poisson analyses and square-root transformation, including the methods used to ‘zero out’ negative changes in HO volume.
- Clarifies the purpose, timing and conduct of the sensitivity analyses.
- Updates the list of subgroups to be studied to be consistent with feedback from FDA.
- Adds analyses for the HO-based secondary analyses and simplifies the analyses of the flare-up-based secondary endpoints.
- Adds summaries of growth velocity.
- Summarizes duration of flare-up treatment and duration of non-flare-up treatment, which are used in the summary of compliance.

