2.1.4 Safety Endpoints

Safety evaluations will include adverse event (AE) and serious AE (SAE) reporting, electrocardiograms, vital signs (temperature, respiratory rate, blood pressure, and heart rate),

physical examination, body weight/BMI, knee and linear height, laboratory parameters (hematology, biochemistry, and urinalysis), urine pregnancy tests for FOCBP, radiographic imaging and whole body computed tomography (WBCT), concomitant medication reporting, and the age-appropriate C-SSRS.

Adverse Event Variables

Adverse Event Observation Periods

- A Pre-treatment AE is an AE with an onset date before the first dose of study drug.
- TEAEs are AEs with (first dose date of study drug) \leq (AE start date) \leq (last dose date of study drug +7 days for all AEs, i.e., non-serious and serious AEs).
 - A chronic TEAE is a TEAE with an onset date during chronic treatment
 - A flare-up TEAE is a TEAE with an onset date during flare-up treatment
- Post-treatment AEs are AEs with a start date $>$ last dose date + 7 days for All AEs (non-serious and serious AEs).

Note that subjects may have multiple independent flare-up treatment cycles, each potentially with associated AEs, within the study.

For the efficacy interim analysis and final analysis, treatment emergence for chronic or flare-up treatment is determined based on the subject's dosing diary. For all other pre-lock analyses, treatment emergence is determined using the subject's planned dosing log if insufficient diary data is available, with the date of the extract of data for the interim analysis used as the end date for TEAE assignment purposes.

Any AE with a missing start date is considered TEAE. For TEAEs that have a partial date where the day is missing, if the month is the same month as a flare-up treatment was given, then the TEAE will be defined as a TEAE associated with flare-up dosing.

All AEs (including SAEs) will be coded using a current or recent version of MedDRA. Adverse event severity will be assessed and reported according to criteria defined in the protocol (mild, moderate, severe). Adverse event causality will also be assessed in terms of relationship to study drug and reported according to criteria described in the protocol (not related, possibly related, probably related, definitely related).

The occurrence of AEs (including SAEs) will be recorded from the time of signed informed consent until the end of the study.

Deaths

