2.4.5 Analysis of Safety Endpoints

Safety analyses will be provided by chronic, flare-up dosing and overall, unless otherwise specified.

General Rules

All safety analyses will be performed on the safety populations defined in [Section 2.3](#), unless otherwise specified, using the following rules:

- The baseline value when summarizing overall visits is defined as the last available value prior to the first chronic dose of study drug.
- The baseline value when summarizing over flare-up visits only is defined as the last available value prior to or on the date of first dose of flare-up treatment within the particular cycle. For the NHS study, the baseline value when summarizing over flare-up visits is defined as the value on the Day 1 visit of the corresponding flare-up.
- The potentially clinically significant (PCS) values for pre specified lab, vital sign and ECG variables are values according to predefined criteria/thresholds (see [Appendix 6.2](#)).
- For AEs, the following conventions for partial or completely missing date imputations will be implemented:

- If the start date is completely missing, the start date is imputed as the date of first dose and the AE is considered treatment emergent and assigned to the chronic dosing period.
- If the day and month of the start date are missing and the start year is the same as the year of first dose, the start date is imputed as the date of first dose and the AE is considered treatment emergent and assigned to the chronic dosing period. If the start year is prior to the year of first dose, the start date is imputed as January 1 of the year and the AE is not considered treatment emergent.
- If the day of the start date is missing and the start month and year is within a period of time within a flare-up treatment, the start date is imputed as the date of the flare-up treatment in the same month as the AE, and the AE is considered treatment emergent and assigned to the flare-up dosing period. Otherwise, if the day of the start date is missing and the start month and year is on or after the date of first dose, the start date is imputed as the date of first dose or the first day of the month of the AE, whichever is later, and the AE is considered treatment emergent and assigned to the chronic dosing period. Otherwise, if the start month and year is before the month and year of first dose, then the start date is imputed as the first day of the month of the AE, and the AE is not treatment emergent.

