Adverse event incidence tables by SOC and PT will be sorted by decreasing frequency incidence of SOC and by decreasing incidence of PT within SOC. The number (n) and percentage (%) of subjects experiencing an AE will be presented by treatment (chronic dosing, flare-up dosing and total palovarotene [overall]). Multiple occurrences of the same event in the same subject will be counted only once. The denominator for computation of percentages is the safety population for the chronic dosing and overall group and the number of subjects in the safety population with flare-up dosing for the flare-up dosing group. TEAEs by Pediatric Subjects (<18 years) and Adult Subjects (≥18 years) are summarized

The following TEAE summaries will be generated for the safety populations:

Analysis of Treatment-Emergent Adverse Events

- Overview of TEAEs, summarizing number (%) of subjects with
 - TEAEs
 - TEAEs possibly related to treatment
 - TEAEs by maximal severity
 - Treatment-emergent SAEs
 - Treatment-emergent SAEs possibly related to treatment
 - TEAEs leading to dose modification or interruption of study drug
 - TEAEs leading to permanent study drug and study discontinuation
 - TEAEs leading to death
- All TEAEs by primary SOC and PT, showing number (%) of subjects with at least one TEAE
- All TEAEs with incidence $\geq 5\%$ in the overall group by primary SOC and PT.
- All TEAEs by maximal severity, presented by primary SOC and PT, showing number (%) of subjects with at least one TEAE by severity (i.e., mild, moderate or severe)
- All TEAEs by relationship, presented by primary SOC and PT, showing number (%) of subjects with at least one TEAE by relationship (i.e., not related, at least possibly related)

- All TEAEs leading to Dose Modification of Study Drug
- All TEAEs leading to Dose Interruption
- All TEAEs leading to Permanent Discontinuation of Study Drug
- All TEAEs leading to Study Discontinuation

Analyses of Pre-Treatment AEs

- All pre-treatment AEs by primary SOC and PT, showing number (%) of subjects with at least one pre-treatment AE

Analyses of Post-Treatment AEs

- All post-treatment AEs by primary SOC and PT, showing number (%) of subjects with at least one post-treatment AE
 - Post-treatment SAEs
 - Post-treatment SAEs possibly related to treatment
 - Post-treatment AEs by maximal severity
 - Post-treatment AEs leading to permanent study drug and study discontinuation
 - Post-treatment AEs leading to death

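### Adverse-event percentages for chronic and flare-up dosing stand side by side with no allowance for unequal time in each dosing state

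*SAP*

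**What the plan says.** SAP 2.4.5 presents adverse-event incidence in three columns: "The number (n) and percentage (%) of subjects experiencing an AE will be presented by treatment (chronic dosing, flare-up dosing and total palovarotene [overall". On the percentage base it says: "The denominator for computation of percentages is the safety population for the chronic dosing and overall group". For the third column the base is "the number of subjects in the safety population with flare-up dosing for the flare-up dosing group". Repeats are collapsed: "Multiple occurrences of the same event in the same subject will be counted only once". Protocol 8.5.3.1 likewise counts first occurrences only.

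Events are placed by onset date. SAP 2.1.4 states: "A flare-up TEAE is a TEAE with an onset date during flare-up treatment". For an event with no start date at all, SAP 2.4.5 says "the AE is considered treatment emergent and assigned to the chronic dosing period". An event missing only the day, in a month with flare-up treatment, goes to the flare-up column.

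SAP 2.4.3 summarises the duration of chronic and of flare-up dosing, but apart from the event counts. SAP 2.4.8 and 2.4.9 define treatment days per subject in each state. No section divides event counts by these durations, and no test between the columns is planned.

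**The concern.** A percentage of subjects with an event grows with time at risk. Here the two columns cover very different lengths of time, and the flare-up length varies between subjects with the number of courses, extensions and restarts. The difference between columns therefore mixes hazard with duration.

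This matters because safety is a primary objective (Protocol 2.1), and the dose relation is a live question. Protocol 1.1.3.2.3 reports that mucocutaneous events became more frequent and more severe with increasing dose. It also reports that the risk of premature epiphyseal fusion appeared higher after the flare-up regimen. The chronic, flare-up and overall split is the SAP's own default for safety analyses. Since V1.2 the general adverse-event tables also carry the retinoid events: "Removes summaries of retinoid-associated AEs, as they already appear in the AE tables".

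The SAP does allow for unequal time elsewhere. New HO volume is annualised (2.1.3), and the flare-up rate is modelled with a log follow-up offset (2.4.4).

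**Working it through.** The documents state no adverse-event rate or hazard, so there is no figure to reproduce. What follows shows how the planned display behaves under stated assumptions.

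**Inputs**
- Flare-up course: 28 + 56 = 84 days (Protocol 6.4).
- Period: 24 months for Part A, taken as 730 days (Protocol 3.1).
- Courses per subject: not given as a forecast. Protocol 7.2.6, when estimating blood volume, spans no flare-ups to "two expected flare-ups treated per year", which is up to four in 24 months.
- Assumed: chronic hazard h = 0.0005 per day, flare-up hazard 3h, both constant.

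**Formulas**, for k courses: Tf = 84k; Tc = 730 − Tf; chronic % = 1 − exp(−h·Tc); flare-up % = 1 − exp(−3h·Tf).

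| Courses | Tc, Tf (days) | h·Tc | 3h·Tf | Chronic | Flare-up | Ratio |
|---|---|---|---|---|---|---|
| 1 | 646, 84 | 0.323 | 0.126 | 27.6% | 11.8% | 0.43 |
| 2 | 562, 168 | 0.281 | 0.252 | 24.5% | 22.3% | 0.91 |
| 4 | 394, 336 | 0.197 | 0.504 | 17.9% | 39.6% | 2.2 |

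The hazard ratio is 3 in every row. Person-time rates would be 0.0005 × 365.25 × 100 = 18.3 and 3 × 18.3 = 54.8 per 100 person-years in these three rows, by construction. With equal hazards and one course, the percentages are 27.6% against 4.1% (1 − exp(−0.042)), although both rates are 18.3.

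**General behaviour.** For rare events the percentage ratio tends to 3Tf/Tc. It falls below 1 when flare-up time is under a quarter of the period (730/4 = 182.5 days) and below 0.5 when it is under a seventh (730/7 = 104 days).

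**Range**
- The chronic denominator includes subjects never given flare-up dosing. If 30% to 70% are flare-up dosed (assumed), with one course in 24 months and chronic hazards of 5 to 20 per 100 person-years, the ratio is 0.37 to 0.42.
- Over 48 months (1,461 days), the rare-event ratio is 252/1377 = 0.18 for one course and 504/1293 = 0.39 for two.
- Over 18 months with one course it is 252/464 = 0.54.
- Under-14s stopped dosing on 4 December 2019. SAP 1.4 anticipated the third interim in mid-May 2020, timed for when all subjects reached 18 months. The last subjects therefore enrolled around mid-November 2018, about 384 days before the hold. One course then gives 252/300 = 0.84.

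**The case against.** The strongest reply is that the most striking row is only one scenario. A reader might infer that the flare-up column will show less than half the chronic incidence at three times the hazard. The documents do not support that as an expected result. It needs about one course in a full 24 months. At two treated flare-ups per year the flare-up column is the higher one. Extensions and restarts lengthen flare-up time, and the dosing interruptions shorten chronic time. This stands: the figures illustrate and do not predict.

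Three other inferences also go too far:
- **That this is the only contrast between dose levels.** SAP 2.4.5 also reports potentially clinically significant laboratory and vital-sign values by dosing state, and bone safety has its own imaging and growth analyses.
- **That the 7-day rule in SAP 2.1.4 is inconsistent** because no such window applies at step-down. The rule separates treatment-emergent from post-treatment events once drug stops; the chronic and flare-up split classifies subjects still on drug. Protocol 1.1.3.2.1 gives a half-life of about 8 hours. A step-down window is at most an optional sensitivity analysis.
- **That dropping the retinoid summaries removed an exposure adjustment.** Nothing shows they had one.

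It is also fair that person-time rates are not a clean measure of dose effect. If first onsets cluster soon after a dose starts or rises, a rate dilutes the long chronic period and inflates short courses. The same subjects enter both columns, and the flare-up itself triggers the higher dose. These points call for a footnote, but the percentages share the overlap and the confounding and add the duration problem.

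Finally, exposure durations are reported. A mean duration in another table does not, however, let a reader recover a first-event rate for a given term.

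**Conclusion.** The point holds as a limitation of the planned display. SAP 2.4.5 sets percentages over unequal and variable time side by side, and no exposure-adjusted adverse-event rate is planned. In the illustration a hazard ratio of 3 appears as 0.43, 0.91 or 2.2 for one, two or four courses. Its size and direction in the trial are unknown, because they rest on course counts, hazards and exposure that the documents do not give. The illustration also assumes constant hazards, full-length courses without extension, and no interruption. No test depends on these columns, so the consequence is a descriptive table that can mislead on dose relation. That is worth correcting for a primary safety objective.

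**What to change.** In SAP 2.4.5, for adverse-event tables still to be produced, add exposure-adjusted incidence beside n (%) in the chronic and flare-up columns: subjects with a first event per 100 person-years at risk in that dosing state. Do this at least for the overall and serious-event summaries, the mucocutaneous terms, and events leading to dose modification.

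Build time at risk from the dosing diary dates already used to assign events, and from the durations in SAP 2.4.8 and 2.4.9, stopping at the first event. Treat interruption days alike in numerator and denominator. SAP 2.4.9 subtracts flare-up duration already net of missed days, so as written it may leave missed flare-up days in chronic time; settle this first.

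Footnote that the rates assume a roughly constant hazard, that the same subjects appear in both columns, and that the flare-up itself confounds the contrast.

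The cost is SAP wording and programming, with no new data. SAP 3.3 says interim-report analyses are not planned to be rerun, so the change need not reopen them.

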#### **8.5.5 Clinical Laboratory Findings**

Change in clinical laboratory findings, vital signs, and other continuous safety parameters will be assessed descriptively, with pre-treatment, on-treatment, and change from pre-treatment values calculated. For purposes of this analysis, pre-treatment will be the last values prior to initiation of chronic dosing.

Group-mean plots (mean and standard error) over time will be provided.

The number and percentage of subjects with potentially clinically significant (PCS) values will be summarized. A focus will be on new-onset PCS values, ie, subjects with pre-existing PCS values at pre-treatment will not be considered to have new-onset values on-treatment.

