the treatment period will be summarized. One summary table will be presented for all chronic visits (non-flare-up visits in the NHS) and for flare-up treatment visits. For derivation purposes for chronic visits, the baseline value for the MOVE trial is the last available value prior to or on the date of first dose of chronic treatment. For the NHS study, the baseline value is the value taken on the Day 1 visit. For flare-up summaries, the baseline value for the MOVE trial is the last available value prior to or on the date of first dose of flare-up treatment with the cycle. For the NHS study, the baseline value is the value taken on the Day 1 visit of the corresponding cycle.

A focus will be on new-onset PCS values, i.e., subjects with pre-existing PCS values at baseline will not be considered to have new onset values after start of study drug. Pre-treatment was defined as the last value prior to initiation of chronic treatment. For flare-up treatment, PCS will be summarized at the subject-level and the flare-up level. Flare-up analyses may include subjects multiple times as a subject may have more than one flare-up treatment cycle within the study, whereas the subject-level analyses will include each subject once, summarizing at least one post-baseline PCS abnormality across all flare-up cycles.

All PCS values will be presented in a subject-based separate listing as well including baseline values, PCS values and follow-up values.

Pregnancy test results for females of child-bearing potential were provided as subject listings.

Analyses of ECG Variables

The summary statistics of all ECG variables (ECG values and changes from baseline) will be calculated for each visit. Mean heart rate, RR, PR, QRS, QT, QTcF, and QTcB will be determined using centralized readings.

Absolute QTc interval prolongation QTcF, and QTcB will be summarized at baseline and post-baseline, using counts of subjects and the following criteria:

- QTc interval >450 msec
- QTc interval >480 msec
- QTc interval >500 msec
- QTc interval increases from baseline >30 msec
- QTc interval increases from baseline >60 msec

The incidence of ECG abnormalities at any time (see [Section 0](#) for the abnormality list) during the treatment period will be summarized by visit and category (rhythm, conduction, morphology/chamber enlargement, axis deviation, myocardial infarction, ST Segment/T waves/U waves).

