New onset ECG PCS values will be summarized for chronic treatment visits. Subjects with pre-existing ECG PCS values at baseline will not be considered to have new onset values after start of study drug. PCS will be summarized at the subject-level. For flare-up treatment, PCS will be summarized at the subject-level. The PCS list is provided in [Appendix 6.2](#).

All PCS values will be presented in a subject-based separate listing as well including baseline values, PCS values and follow-up values.

All ECG abnormalities (rhythm, conduction, morphology/chamber enlargement, axis deviation, myocardial infarction, ST Segment/T waves/U waves), with specific abnormality will be provided in a by subject listing.

Analyses of Vital Sign Variables

The summary statistics of all vital sign variables (vital signs values and changes from baseline) will be calculated for each visit. Summary tables will be provided for all treatment visits, both chronic and flare-up visits. For these tables, the baseline value for the MOVE trial is the last available value prior to or on the date of first dose of chronic treatment. For the NHS study, the baseline value is the value taken at the Day 1 visit. Summary tables will also be provided for flare-up treatment visits only using date of flare-up dosing to derive change from baseline. For flare-up treatment, subjects may contribute more than one observation for summaries due to multiple cycles of flare-up treatment. Each cycle of flare-up treatment will be summarized separately. For these tables, the baseline value for the MOVE trial is the last available value prior to or on the date of first dose of flare-up treatment within the cycle. For the NHS study, the baseline value is taken at Day 1 of each individual flare-up.

The incidence of PCSs at any time (see [Appendix 6.2](#) for the PCS list) during the treatment period will be summarized in the same manner as lab PCS tables.

All PCS values will be presented in a separate listing as well.

Analyses of C-SSRS Variables

The palovarotene treated and NHS untreated subjects who report any type of suicidal ideations in the Columbia-Suicide Severity Rating Scale (C-SSRS) or any suicidal behavior during the study will be presented in listings.

A tabular summary of subjects with any type of suicidal ideation or behavior will be presented.

A listing will summarize any subject with Type 4 or 5 suicidal ideation or any suicidal behavior.

Analysis of Hearing Assessments

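### The SAP resets the reference for new-onset lab and vital-sign abnormalities at each flare-up cycle, contrary to the protocol, so some that arise on chronic drug can count as new onset in neither summary

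*SAP*

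**What the plan says.** Protocol 8.5.5 puts the focus of the PCS analysis on new-onset values and gives one reference point: "For purposes of this analysis, pre-treatment will be the last values prior to initiation of chronic dosing". It has no separate reference for flare-up treatment.

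SAP 2.4.5 (Analyses of Laboratory Variables) splits the PCS incidence: "One summary table will be presented for all chronic visits (non-flare-up visits in the NHS) and for flare-up treatment visits". Each part has its own baseline. For the chronic part: "For derivation purposes for chronic visits, the baseline value for the MOVE trial is the last available value prior to or on the date" (meaning the day chronic dosing starts). For the flare-up part: "For flare-up summaries, the baseline value for the MOVE trial is the last available value prior to or on the date of first dose" (meaning the cycle's first flare-up dose). The General Rules of the same section say this baseline is taken afresh each time: "prior to or on the date of first dose of flare-up treatment within the particular cycle".

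The new-onset rule comes next: "subjects with pre-existing PCS values at baseline will not be considered to have new onset values after start of study drug". The sentence after it is "Pre-treatment was defined as the last value prior to initiation of chronic treatment", which agrees with the protocol and not with the reset.

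Vital-sign PCS incidence is tied to the laboratory rule: "during the treatment period will be summarized in the same manner as lab PCS tables".

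SAP 1.9 and 1.10, which list statistical changes to the protocol and to the SAP, do not mention a change of reference for new-onset PCS.

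**The concern.** New-onset PCS incidence is a main planned summary of laboratory and vital-sign harm. A subject starting a flare-up cycle has normally been on daily palovarotene for some time, so the reset baseline is an on-drug value. If the drug has already produced an abnormality by then, the flare-up summary treats it as pre-existing. The chronic summary covers chronic visits, and the Flare-up Cycle Safety Day 1 sample is not one. A drug-related abnormality first detected at that sample could therefore fall between the two summaries. Its persistence or worsening at the higher flare-up doses would also be absent from the flare-up new-onset count.

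The text also does not settle which reference governs new onset. Two programmers following the same paragraph could produce different tables.

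**Working it through.** The plan gives no figure to reproduce, so the check applies the literal rule to test cases and then asks how far it could reach.

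**Inputs.**
- Chronic labs are 6-monthly (Protocol 7.2.6) and chronic vital signs 3-monthly (7.2.4).
- Both are also taken at Flare-up Cycle Safety Day 1 and every 12 weeks after that.
- Flare-up visits have a window of ±4 days (Protocol Table 2, footnote 1).
- Day 1 labs are waived if results within the previous month were normal or not clinically significant (Table 2, footnote 4).
- Labs carrying a flare-up visit label are assigned to a flare-up cycle (SAP 2.4.5, General Rules).
- The protocol's planning figure is two treated flare-ups per year (7.2.6).

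**Rule as coded.** Chronic summary: new onset if the pre-chronic value is not PCS and any later chronic-visit value is. Flare-up summary: new onset if the last value on or before the first flare-up dose is not PCS and any later flare-up-visit value is. In every case the pre-chronic value is normal.

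| Case | Chronic | Flare-up | Single pre-chronic baseline, all visits |
|---|---|---|---|
| A. PCS on the Day 1 dose date, resolved by Week 12 | no | no | yes |
| A2. PCS on Day 1 and at Week 12, gone by the next chronic visit | no | no | yes |
| B. PCS on Day 1, persists to the next chronic visit | yes | no | yes |
| C. Day 1 sample drawn 3 days after the first flare-up dose | no | yes | yes |
| D. First seen at a chronic visit within a month before the flare-up | yes | no | yes |

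A concrete A2: triglycerides are 150 mg/dL before the study, 450 on the Day 1 dose date, still above the PCS limit of 400 (SAP Appendix 6.2) at Week 12, and below it at the next chronic visit. Neither summary counts a new onset. In case C the event is counted, but an onset during chronic dosing is attributed to flare-up dosing.

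Some vital-sign criteria in Appendix 6.2 are changes from baseline. In subjects over 12, a systolic rise of 25 mm Hg reached partly before and partly during the cycle meets the criterion against the pre-chronic value but not against the Day 1 value.

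**Reach.** With two treated flare-ups a year, one per cycle and no extensions, 48 months gives 8 chronic, 8 Day 1 and 8 Week 12 lab draws. Day 1 draws are then 8/24 = 33% of post-baseline draws. If 1 in 6 is waived (one month of each six-month interval, flare-ups falling at random), 8 × 5/6 = 6.7 remain, and 6.7/22.7 = 29%.

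**Illustrative simulation.** Onsets are uniform over chronic-dosing time in 24 months. Labs are at Months 6, 12, 18 and 24. Gaps between cycles are exponential with mean 12/r months, for r = 1 or 2 cycles per chronic-dosing year. Each cycle lasts 84 days, and every Day 1 sample is drawn on the dose date.
- First scheduled draw after onset is a Flare-up Day 1: 21% (r = 1) to 37% (r = 2).
- Present at Day 1 but at no chronic visit: 7% to 13% if the abnormality lasts 1 month, 11% to 20% if 3 months, 0% if 6 months.
- Allowing for the one-month waiver lowers these by no more than about two percentage points.

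**The case against.** A reader might infer that every abnormality first seen at Flare-up Day 1 is lost from both summaries, or vanishes from the report. The documents do not support that. Case B is counted in the chronic summary and case C in the flare-up summary. SAP 2.4.5 also lists every PCS value by subject with baseline and follow-up values, and Protocol 7.2.6 has clinically significant post-baseline results recorded as adverse events.

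The sentence defining pre-treatment directly follows the new-onset rule and can be read as governing it, in which case the reset would not apply to new onset at all. That reading is possible, but the SAP does not choose between the two, so the wording still needs settling.

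The SAP's General Rules promise safety analyses by chronic dosing, flare-up dosing and overall unless otherwise specified, with a pre-chronic baseline for the overall view, and the laboratory text refers to PCS incidence at any time in the treatment period. An all-visit new-onset table may therefore be intended. The PCS text, however, derives baselines only for chronic and flare-up visits and names no overall new-onset table. The listing gives no incidence.

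A within-cycle baseline is legitimate. It isolates change during higher dosing and parallels the natural history study's flare-up Day 1 baseline. This stands, and is a reason to keep it, though not as the only reference for flare-up visits.

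A reader might also infer a downward bias in reported harm of the simulated size. That is not supported either. The durations and cycle rates are assumptions. The shares count abnormalities, whereas part of the summary is by subject, and a subject with another qualifying value still counts. End-of-treatment labs are left out. Vital signs have 3-monthly chronic visits, so fewer of those would be missed. The reset can also add counts: a subject who is PCS before chronic dosing, normal at cycle start and PCS afterwards is new onset under the reset but not under the protocol.

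**Conclusion.** The concern holds in a conditional form. The SAP's flare-up reference for new-onset PCS, for labs and by extension vital signs, conflicts with Protocol 8.5.5 and with a neighbouring sentence in the SAP itself. Under the literal rule, an abnormality arising on chronic drug can be missed by both summaries when two conditions are met: the first abnormal sample is dated on or before the first flare-up dose, and the abnormality has gone by the next scheduled chronic visit. Even if it persists or worsens during flare-up dosing, the flare-up summary omits it. One pre-chronic baseline over all visits counts all five test cases.

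The simulated 7% to 20% for abnormalities of 1 to 3 months shows that the gap need not be negligible under plausible inputs. It does not estimate the trial's error. The net effect on subject-level incidence is unknown in size and direction.

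**What to change.** In SAP 2.4.5:

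1. State that new-onset PCS for laboratory values and vital signs is judged against the last value before the first chronic dose, as in Protocol 8.5.5.
2. Add one new-onset PCS table over all on-treatment visits, chronic and flare-up, with Flare-up Cycle Safety Day 1 values explicitly included. If the overall default in the General Rules is meant to provide this, say so.
3. Keep the within-cycle baseline as a companion shift summary, labelled as such, and show in it any worsening among subjects already PCS at cycle start.

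The cost is a wording change and one extra table, with no new data. Reported PCS incidence may come out slightly higher.
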